8.2.6 Change From Baseline

Change from baseline will only be calculated for measures that have post-baseline records.

Change from baseline will be calculated as:

- visit value – baseline value.

Percentage change from baseline will be calculated as:

- $(\text{change from baseline} / \text{baseline value}) * 100$

8.2.7 Multiple Assessments

All data will be reported according to the nominal visit date/time for which it was assessed (that is, no visit windows will be applied during dataset creation).

If multiple assessments for the same visit occur, it will be distinguished why this is the case. If a laboratory sample was repeated due to technical problems the results from the valid sample(s) for this visit – the non-missing results – will be used in the analysis. If a laboratory sample was repeated as safety follow-up to monitor abnormal values of the initial sample, the initial sample (revealing the abnormal values) of this visit will be used in the analysis.

Data from all assessments (scheduled and unscheduled), including multiple assessments, will be included in listings.

8.2.8 Actual Treatment

The subjects' actual treatment will be derived from exposure data. If a subject's actual treatment is the same as the assigned treatment, then actual treatment is the assigned treatment. If a subject receives a study treatment that is different from the assigned treatment for the entire time of treatment, then actual treatment is the different treatment (the treatment actually received).

8.2.9 Derived Variables

Start and End of Retreatment Periods

Neither the start and end date of optional Retreatment Period(s) nor the number of individual Retreatment Period(s) will be explicitly recorded in the eCRF. So, the start date of a Retreatment Period will be derived by using the visit date associated with the label of first visit in a Retreatment Period, ie using a visit label of "RT – Day 1 (x)", x – counter of individual Retreatment Period. The end date of a Retreatment Period will be derived in the same way by using the last available date in a chronological order of visit labels in a Retreatment Period, ie using a visit label of "RT – Day 182 (x)", x – counter of individual Retreatment Period. The individual number of Retreatment Period will be derived from the counter (in brackets) given in the visit label of Retreatment Periods.

For analysis purpose, a Retreatment Period will start with the first documented study drug intake on or after first retreatment visit which was identified via the visit label. The end of the Retreatment Period will be identified in a similar way. It will be the last intake of study drug before or on the last retreatment visit which was identified via the visit label.

Demographics

Years of Age

Years of age will be derived as the number of complete years between a subject's birth date and the date of informed consent.

Body mass index

Body mass index (BMI) will be derived using the following formula:

$$\text{BMI (kg/m}^2\text{)} = \text{Weight (kg) / [Height (m)]}^2$$

The height at Screening and the dry weight obtained from the medical history will be used. If the dry weight is missing, the weight at Screening will be used. If the weight at Screening is missing, the Day 1 weight will be used.

Efficacy

Estimated glomerular filtration rate (eGFR)

eGFR will be derived using the following MDRD formula [Levey et al, 2008]:

$$\text{eGFR (mL/min/1.73m}^2\text{)} = [(175) \times (\text{standardized } S_{\text{cr}}^{-1.154}) \times (\text{age}^{-0.203}) \times (1.212, \text{ if black}) \times (0.742, \text{ if female})]$$

The serum creatinine (S_{cr}) is expressed as mg/dL. The years of age will be derived based on the subject birth date and the date that the S_{cr} sample was taken.

eGFR at the End of Treatment Period 1 (End-of-TP1)

The mean of Week 11 and Week 12 eGFR measurements. If one of the measurements is missing it is then the non-missing value.

eGFR at the End of Treatment Period 2 (End-of-TP2)

The mean of Week 36 and Week 38 eGFR measurements. If one of the measurements is missing it is then the non-missing value.

Response to Open-Label C1-INH at End of Treatment Period 1 (End-of-TP1)

Responders are defined as subjects whose End-of-TP1 (the mean of Week 11 and Week 12) eGFR $\geq 90\%$ of baseline and ≥ 20 mL/min/1.73 m². The baseline eGFR is defined as the mean of the screening and Day 1 values in [Section 8.2.5](#).

Loss of Response During Treatment Period 2

Loss-of-response at the End-of-TP2 is defined as any 1 of the following 3 conditions:

- End-of-TP2 eGFR (mean of Week 36 and Week 38 eGFR) that is not stable, defined as:
 - End-of-TP2 eGFR that is $< 90\%$ of the End-of-TP1 eGFR for subjects whose End-of-TP1 eGFR (mean of Week 11 and Week 12 eGFR) is $\geq 100\%$ of baseline;

- End-of-TP2 eGFR that is < 90% of baseline for subjects whose End-of-TP1 eGFR is ≥ 90% of baseline and < 100% of baseline.
- Allograft failure (defined by allograft nephrectomy, or institution of permanent dialysis, or return to the transplant waitlist for renal transplant, whichever occurs first)
- Subject death by any cause.

All-Cause Allograft Failure

All-cause allograft failure within 48 months after enrollment is defined as 1 of the following, whichever occurs first:

- Allograft failure (defined by allograft nephrectomy, or institution of permanent dialysis, or return to the transplant waitlist for renal transplant, whichever occurs first), OR
- Subject death by any cause.

No subject has reached 48 months after enrollment due to study termination.

8.3 Study Periods Relative to Treatment

8.3.1 Time in Relation to Treatment

Safety data (AEs and concomitant medications) will be assigned to the study time periods defined below (refer to [Section 8.1.2](#) for imputation of incomplete or missing dates).

Before-therapy is defined as the date/time prior to the first start of subject's infusion with study treatment.

On-therapy is defined as the time from the first start of an infusion of study treatment in Treatment Period 1 up to 30 days after last study drug administration in Treatment Period 2. If a subject had a Retreatment Period, the time still on drug in Retreatment Period (extended to +30 days after last drug in Retreatment Period) will be accounted as On-therapy. In case a subject has more than one Retreatment Periods, the time between Retreatment Periods will be accounted for Follow-up.

Follow-up is defined as any time after last study drug administration in Treatment Period 2 plus 30 days. Time of Retreatment Periods are to be excluded from Follow-up, please refer to On-therapy.

8.3.2 Study Time Periods for AEs

AEs occurring On-Therapy or during Follow-up will be handled as treatment-emergent AEs.

8.3.3 Study Time Periods for Prior and Concomitant Medications

Prior medications are those ending in the before-therapy period.

Concomitant medications include those that start during the before-therapy period and continue into the on-therapy and Follow-up periods as well as those that start during the on-therapy and Follow-up time periods. Therapies that start during the before-therapy period and have a missing end date will be assumed to continue into the on-therapy period and, therefore, will also be considered concomitant medications.

9 Study Population

Only data of subjects who provided informed consent (informed consent date available in the database) will be included in the statistical analysis.

Unless otherwise stated, all tables and listings in this section will be based on the mITT and / or Safety Analysis Set, and all summaries and data listings will use treatment descriptors as specified in [Section 7.2](#).

9.1 Disposition of Subjects

The following summaries will be provided by treatment group and for the Screened Analysis Set, as appropriate:

Subject disposition presenting the number and percentages of:

- subjects screened,
- subjects ineligible/failed screening,
- reason for screening failure,
- subjects eligible for Treatment Period 1,
- subjects treated with open-label study medication in Treatment Period 1,
- subjects completed Treatment Period 1,
- subjects discontinued during Treatment Period 1 (before Week 13) and reasons for discontinuation,
- subjects eligible for randomization in Treatment Period 2 (subjects reached week 13 and responded to treatment in Treatment Period 1),
- subjects randomized,
- subjects treated with blinded study medication during Treatment Period 2,
- subjects completed Treatment Period 2,

- subjects discontinued during Treatment Period 2 (before Week 38) and reasons for discontinuation,
- Subjects discontinued from study before week 208,
- subjects available by visit (Treatment Period 1, Treatment Period 2), a subject will be considered to have attended a visit if a visit date is recorded (provided for RiS Analysis Set and RWS Analysis Set).

Number and percentage of subjects in the following analysis sets will be presented:

- Screened Analysis Set,
- Enrolled Analysis Set,
- RiS Analysis Set,
- RWS Analysis Set,
- mITT Analysis Set,
- PK Analysis Set,
- CCI [REDACTED]

Number and percentage of subjects in the following categories will be presented:

- Subjects applicable to original protocol,
- Subjects applicable to amendment 1,
- Subjects applicable to amendment 2,
- Subjects applicable to amendment 3.

Reasons for study withdrawal will be presented in the order they are displayed in the eCRF.

A listing will be provided including date of informed consent, date of randomization, date of first treatment (Treatment Period 1, Treatment Period 2, Retreatment Period[s]), study completion, reason if not completed, and assignment to analysis sets.

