10.2.4 Modified Intent-to-Treat Analysis Set

All subjects randomized under the original protocol and under all protocol amendments will be included in this population except the subjects randomized prior to amendment 3 who do not satisfy the criteria in amendment 3. This modified ITT set will be the primary analysis set for the analysis of efficacy data.

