10.3 Statistical Analyses and Methods

A complete description of the statistical analyses and methods will be available in a statistical analysis plan, which will be finalized before the database is locked.

Unless otherwise stated, efficacy analyses will be based on the modified ITT analysis set for analyses of endpoints defined in TP2. Sensitivity analyses will be based on the ITT set.

Enrolled analysis set will be used for the analysis of endpoints defined over the entire study. Sensitivity analyses of these endpoints will be done with ITT and modified ITT sets.

Safety will be summarized over the entire study, and according to treatment period. Safety will be analyzed for either the RiS analysis set or the RWS analysis set, as appropriate.

All data will be summarized in tables or figures and all ICH-required data in the database will be listed. Unless otherwise specified, continuous variables will be summarized by presenting the number of non-missing observations, mean, standard deviation, median, minimum and maximum. Other descriptive statistics (eg, 25th and 75th percentile, coefficient of variation) will be reported when appropriate. Categorical variables will be summarized by presenting the number of subjects and percentage for each category.

Unless otherwise stated, the statistical model on which inference is based will contain terms for the randomization strata as well as treatment. It is anticipated that subject accrual will be spread thinly across the centers. There will be no pooling of centers for purposes of analysis. Therefore, investigation of center-by-treatment interaction will not be possible.

Unless otherwise specified, all confidence intervals and *P*-values will be two-sided. From a formal inferential perspective, the type I error will be fully allocated to the analysis of the primary efficacy variable, and the selected secondary efficacy variable (ie, all-cause allograft failure after randomization into TP2 and through the Responder Follow-up Period). A serial gatekeeper hierarchical testing strategy will be used to protect the overall type I error rate of 0.050 (two-sided). Statistical significance will be claimed only when the results of the two-sided test favor C1-INH.

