10.3.3 Efficacy Analyses

All efficacy endpoints will be analyzed based on Modified-ITT analysis set. Sensitivity analyses for efficacy endpoints will be based on ITT set.

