6.3 Intent-to-Treat Analysis Set

The Intent-to-Treat (ITT) analysis will comprise all subjects who were randomized. Subjects will be classified according to the investigational product to which they were assigned (ie, continued C1-INH or placebo) regardless of what was actually received. This will be the primary analysis

set for the analysis of efficacy data. Any subject who received a randomization identification number will be considered to have been randomized.

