6.4 Modified Intent-to-Treat Analysis Set

All subjects randomized under the original protocol and under all protocol amendments will be included in the Modified ITT (mITT) population except the subjects randomized prior to Amendment 3 who did not satisfy the eligibility criteria updated in Amendment 3. The mITT Analysis Set will be the primary analysis set for the analysis of efficacy data.

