10.1 Analysis of Proportion of Subjects With Loss of Response at the End-of-TP2

The number and proportion of subjects with loss of response at the End-of-TP2 will be presented by treatment group along with the confidence interval for the difference between the two groups.

Subjects will be considered to have lost response if they drop-out or are lost to follow-up before the response status at the End-of-TP2 could be determined.

Components of loss-of-response at the End-of-TP2 will be summarized by treatment groups in terms of the proportion of subjects with:

- End-of-TP2 eGFR (mean of Week 36 and Week 38 eGFR values) that is not stable, defined as:
 - End-of-TP2 eGFR that is < 90% of the End-of-TP1 eGFR for subjects whose End-of-TP1 eGFR is \geq 100% of baseline,
 - End-of-TP2 eGFR that is < 90% of baseline for subjects whose End-of-TP1 eGFR is \geq 90% of baseline and < 100% of baseline,
- All-cause allograft failure (ie, allograft nephrectomy, or institution of permanent dialysis, or return to the transplant waitlist for renal transplant),
- Death by any cause.

The primary efficacy analysis will be conducted for the mITT Analysis Set.

10.1.1 Subgroup Analyses of Proportion of Subjects With Loss of Response at the End-of-TP2

The proportion of subjects with loss of response at the End-of-TP2 will be summarized by the treatment group for the following subgroups based on the following subgroup analyses outlined below will be conducted for the mITT Analysis Set.

The following subgroups, and possibly others to be described in the SAP, will be summarized by treatment group with respect to the proportion of loss-of-response:

- Geographic region: USA, non-USA,
- DSA by randomization strata: sensitized, de novo,
- DSA by classification: HLA class I, HLA class II, both HLA class I and II,
- AMR severity: severe, non-severe (all other severities),
- Type of donor: deceased, living,
- Recipient race: Black, non-Black,
- Recipient sex: Male, Female,
- Recipient age: < 65 years, \geq 65 years.

The difference in the proportion of response along with the 95% confidence interval will be also presented for each subgroup.

10.2 Analysis of key Secondary Endpoint Proportion of Subjects With All-Cause Allograft Failure Through the Responder Follow-up Period (ie, Within 48 Months After Enrollment)

No subject will complete the follow-up period of 48 months after enrollment. Therefore, this key secondary analyses cannot be conducted.

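### The SAP specifies no ITT efficacy output, although the protocol promises ITT sensitivity analyses, and it names both ITT and mITT as the primary efficacy set

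*SAP*

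**What the plan says.** **Protocol.** Section 10.2.4 states: "This modified ITT set will be the primary analysis set for the analysis of efficacy data". Section 10.3 adds, for endpoints defined in Treatment Period 2 (TP2): "Sensitivity analyses will be based on the ITT set". Section 10.3.3 repeats it for efficacy as a whole: "Sensitivity analyses for efficacy endpoints will be based on ITT set". The synopsis says the same.

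**SAP, definition of the sets.** Section 6.3 says of ITT: "This will be the primary analysis" set for efficacy data. Section 6.4 says: "The mITT Analysis Set will be the primary analysis set for the analysis of efficacy data". The mITT set is all randomized subjects "except the subjects randomized prior to Amendment 3 who did not satisfy the eligibility criteria updated in Amendment 3".

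**SAP, use of the sets.** Section 10 bases TP2 efficacy summaries and the efficacy subject listings on mITT. Section 10.1 states: "The primary efficacy analysis will be conducted for the mITT Analysis Set". No section specifies an efficacy table or listing on ITT. The one analysis rule that still names ITT is a denominator convention in 8.1.1, with no ITT output attached to it.

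**SAP, disposition and changes.** Section 9.1 says "Number and percentage of subjects in the following analysis sets will be presented" and then names Screened, Enrolled, RiS, RWS, mITT, PK and one redacted set. Section 5 itemizes the endpoints that lose their analysis after termination. The ITT sensitivity analysis is not among them. A closing sentence says only that the analysis of other endpoints was reduced as the later sections describe.

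**The concern.** The mITT set removes subjects after randomization, using criteria finalized after those subjects were randomized. The ITT sensitivity analysis is the protocol's check on whether that removal affects the result. Early termination does not explain its absence, because SAP 10.1 still produces the loss-of-response table with a confidence interval for the difference, and the same table could be run on ITT from the same data.

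If the SAP is followed as written, the report will contain one estimate, on the set that can lose randomized subjects, and nothing to compare it with. With 13 subjects randomized, a few exclusions could change the picture visibly. The two primary-set sentences add an internal contradiction on the set that the headline estimate rests on.

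**Working it through.** **1. Protocol and SAP side by side**

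| Item | Protocol | SAP |
|---|---|---|
| Primary efficacy set | mITT (10.2.4) | ITT in 6.3; mITT in 6.4 and 10.1 |
| ITT sensitivity analysis | Promised (synopsis, 10.3, 10.3.3) | No ITT efficacy output specified |
| Removal itemized as a change | n/a | Not in section 5; general sentence only |
| ITT in the list of analysis sets | n/a | Absent from the visible 9.1 list |

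**2. What can be recovered from planned output.** SAP 9.1 counts subjects randomized, by treatment group as appropriate. By the 6.3 definition that count is the ITT set. It also counts mITT, so randomized minus mITT gives the number removed. The 9.1 listing shows assignment to analysis sets, and section 7 puts the treatment group on every listing, so the arm is recoverable too. Not planned for an excluded subject: the loss-of-response status, the estimate with that subject included, and the Amendment 3 criterion not met.

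**3. Inputs for the size.** From the documents: 13 randomized (SAP 3); 1:1 allocation and design loss-of-response rates of 0.75 placebo and 0.30 C1-INH (SAP 4.5). As background, the stated power of about 95% with 30 per arm reproduces: 95.7% by the pooled chi-square and 94.5% by the likelihood-ratio chi-square. It is not in dispute.

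Assumed, because the documents do not give them: a 7:6 split, and outcomes near the design rates. 7 × 0.75 = 5.25, taken as 5/7 on placebo; 6 × 0.30 = 1.8, taken as 2/6 on C1-INH. The number excluded, k, is varied from 0 to 3.

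**4. One exclusion, effect on an arm proportion.** Removing a subject changes numerator and denominator together.

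- Placebo 5/7 = 71.4%. Remove a loss: 4/6 = 66.7% (−4.8 points). Remove a non-loss: 5/6 = 83.3% (+11.9).
- C1-INH 2/6 = 33.3%. Remove a loss: 1/5 = 20.0% (−13.3). Remove a non-loss: 2/5 = 40.0% (+6.7).

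The range is about 5 to 13 points. The ceiling is 1/7 = 14.3 or 1/6 = 16.7 points. It is reached only when the removed subject is the only one in the arm with that outcome, for example 6/7 to 6/6 or 5/6 to 5/5.

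**5. Effect on the risk difference (placebo minus C1-INH).** ITT: 5/7 − 2/6 = 0.38. The Wald 95% interval is −0.12 to 0.89, used here for illustration because SAP 10.1 names no interval method. All ways of removing k subjects were enumerated:

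| k excluded | Possible mITT difference | Largest shift from 0.38 |
|---|---|---|
| 0 | 0.38 | 0 |
| 1 | 0.31 to 0.51 | 0.13 |
| 2 | 0.21 to 0.71 | 0.33 |
| 3 | 0.05 to 0.83 | 0.45 |

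The extremes at k = 3 are 5/7 − 2/3 = 0.05 and 5/6 − 0/4 = 0.83. The mirrored split (4/6 placebo, 2/7 C1-INH) gives the same ranges.

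**The case against.** **Excluded subjects are not hidden.** A reader might infer from the missing ITT line in 9.1 that nobody could tell how many subjects were removed or from which arm. The documents do not support that: step 2 shows that both can be recovered. This part of the objection stands, and it limits the gap to outcome, effect and reason. The remaining outputs do not close that gap. The efficacy listings are on mITT. The deviation listings in SAP 9.2 need not show the unmet criterion, because a subject who was eligible under an earlier protocol version did not deviate. General data listings may carry creatinine values, but no derived loss-of-response status is planned for an excluded subject.

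**The reduction was announced.** SAP 3 warns that many protocol analyses cannot be performed, section 5 has its general sentence, and section 10 states mITT openly. So it would be too strong to call the removal undeclared. It is not itemized, and no section says that the ITT analysis was withdrawn.

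**The primary set is obvious.** The protocol and SAP 4.2.1.3, 6.4, 10 and 10.1 all point to mITT, and only one sentence in 6.3 differs. That is fair. The conflict is easily resolved, but a final SAP should not contain it.

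**The stakes are low.** SAP 4.2.1.3 and 7.3 drop all formal testing, the mITT rule comes from the protocol, and the sponsor is blinded during TP2. This also stands. What is affected is the transparency of a descriptive estimate, not type I error.

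**Conclusion.** The point holds as a gap between protocol and SAP. The promised ITT sensitivity analysis has no output in the SAP, its removal is not itemized, ITT is missing from the visible 9.1 list, and two sets are called primary. The redacted 9.1 entry is unlikely to be ITT: ITT is named openly in 6.3, and the redacted entry follows PK just as the redacted section 6.7 follows 6.6.

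The size is conditional. Under the assumed 7:6 split and outcomes of 5/7 and 2/6, one exclusion moves an arm proportion by about 5 to 13 points and the risk difference by up to 0.13. Two or three could move the risk difference by up to 0.33 or 0.45. With no exclusions, ITT and mITT coincide and there is no shift.

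Two stronger readings go beyond the documents. A reader might take 14 to 17 points as the usual effect of one exclusion, but that is the ceiling. A reader might also infer that subjects were in fact excluded or that the reported result is biased. Amendment 3 did revise the responder definition and several eligibility criteria, so exclusions are plausible. The documents do not say that any of the 13 is affected, nor in which direction.

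**What to change.** 1. Delete the primary-set sentence in SAP 6.3, so that mITT is the only primary efficacy set, as in the protocol.
2. Add ITT to the list of analysis sets in SAP 9.1.
3. Repeat the SAP 10.1 loss-of-response table (counts, difference, confidence interval) and its listing on ITT.
4. List each ITT subject excluded from mITT, by arm, with the Amendment 3 criterion not met. If nobody is excluded, one sentence saying that the two sets coincide replaces items 3 and 4.

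The cost is one repeated table and one short listing, with no new data.
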